10.0 EFFICACY INTERIM AND FINAL ANALYSES

This study will have 1 planned efficacy interim analysis and 1 final analysis:

- Interim Analysis (IA – ORR & OS interim and OS events re-estimation): when at least 156 OS events in IMDC Intermediate- or Poor-risk Population have been observed.
- Final Analysis (FA – OS final): timing will be determined at the time of IA using the promising zone adaptive method ([Mehta and Pocock 2011](#)) to estimate the OS events needed.

11.0 DATA MONITORING COMMITTEE

An external multidisciplinary Data Monitoring Committee (DMC) will be convened for this study. The DMC will be comprised of qualified clinicians and a biostatistician, all independent from the Sponsor and (for the clinicians) independent of investigational sites, selected to avoid conflict(s) of interest. The DMC's specific activities will be detailed in a mutually agreed upon charter, which will define the relevant processes, including meeting proceedings and structure, data assessments, documentation and recordkeeping, process for DMC recommendations, and regulatory reporting, as applicable. The charter will contain procedures to ensure the minimization of bias, such as maintaining confidentiality of any interim data.

The DMC will review the results of the interim analyses as well as assess accumulating safety data and emerging risk/benefit balance at regular intervals and on an ad-hoc basis as detailed in the DMC charter. The DMC will also conduct the OS events re-estimation; details will be provided in the DMC charter.

12.0 PHARMACOKINETIC, PHARMACODYNAMIC, [REDACTED] ANALYSIS

In addition to the objectives described in this section, PK data obtained in this study may also be combined with data from other studies to develop population PK models. These models may be used to evaluate the effects of intrinsic and extrinsic covariates on the PK of NKTR-214 related molecules and/or nivolumab and to determine measures of individual exposure for nivolumab (such as single dose and steady state peak, trough and time averaged concentration, CL volume, half-life) and for NKTR-214 (such as AUC, clearance, volume, half-life, C_{max} , C_{min} , and C_{avg}). Model predicted exposures may be used for exposure-response analyses of selected efficacy and safety endpoints. Results of any population PK or exposure-response analyses will be reported separately.

12.1 Pharmacokinetic Analysis

Listings for blood collection dates, times and concentrations will be generated by patient for each analyte. Sampling time deviations will be computed as differences between scheduled (nominal) and actual sampling times and expressed in hours and as a percentage of the nominal time.

Observed plasma NKTR-214-RC, NKTR-214-AC, and Total-PEG, and serum nivolumab concentrations at each nominal PK sampling time will be listed by patient and tabulated for each analyte using descriptive statistics, including but not limited to n (observed), n (non-zero), arithmetic mean, standard deviation (SD), standard error of the mean (SE), arithmetic coefficient of variation (CV%), geometric mean, geometric CV%, median, minimum, and maximum.

Mean (+ standard deviation) observed plasma NKTR-214-RC, NKTR-214-AC, and Total-PEG concentrations versus nominal time plots will be generated on linear and semi-logarithmic scales for each analyte for Cycle 1 based on nominal sampling times. For serum nivolumab, mean (+ standard deviation) serum concentrations versus nominal time will be generated on linear scale by nominal sampling time. Nivolumab concentrations should not be connected by a line as all the samples are pre-dose concentrations from different cycles.

PK samples that were collected outside the protocol accepted time windows will be excluded from summary tables and summary figures.

Rounding for the reporting of descriptive statistics will be to three significant digits, except for n, which will be rounded to the whole value. Percentages such as CV% presented in tables will be rounded to one decimal place.

Descriptive statistics will not be performed if $n < 3$ and summary tables will only include median, minimum, and maximum.

12.1.1 Handling of Missing Values, BLQ, and Outliers

- NKTR-214-RC, NKTR-214-AC, and Total-PEG

When summarizing concentration values, below the limit of quantification (BLQ) values will be considered as zero, and zero values will be excluded from the calculation of geometric means and CV% geometric mean, however, zero values will be included for all other summary statistics and the number of non-zero concentrations will be reported. Listings for concentrations values (except for pre-dose C1D1) will list these concentrations as < lower limit of quantification (LLOQ).

Samples with concentrations 5 x higher than mean + standard deviations (SD) for all samples at that time will be considered outliers and not included in analyses and summary statistics and plots. The reason for not using selected data will be presented and discussed in the clinical study report (CSR).

- Nivolumab

When summarizing concentration values, BLQ values (except for pre-dose C1D1) will be imputed as LLOQ/2. Listings for concentrations values (except for pre-dose C1D1) will list these concentrations as <LLOQ. Pre-dose C1D1 BLQ values will be set to zero, and zero values will be excluded from the calculation of geometric means and CV% geometric mean, however, zero values will be included for all other summary statistics and the number of non-zero concentrations will be reported for pre-dose C1D1.

12.2 [REDACTED]/Pharmacodynamic Analysis

Observed plasma sCD25 and cytokine concentrations, and fold change from baseline at each nominal PK sampling time and maximum fold change and time of maximum fold change will be listed by patient and tabulated for each analyte using descriptive statistics, including but not limited to n (number of non-missing data), arithmetic mean, standard deviation, SE, arithmetic CV%, geometric mean, geometric CV%, median, 25th and 75th percentiles, minimum, and maximum.

For sCD25, all Cycle 1 pre-dose concentrations that are BLQ will be set to 0, all other concentrations that are BLQ will be considered missing. Zero values will be excluded from the calculation of geometric means and CV% geometric mean. Missing concentration values will not be included in the descriptive statistics.

For each cytokine, all BLQ values will be set to the lower limit of quantification (LLOQ).

Plot of mean (+SE) plasma sCD25 and cytokine concentrations versus nominal time will be generated for each analyte for baseline and Cycle 1. Fold change from baseline plots will also be generated. Baseline is the last observation prior first dose of study drug within 2 weeks (or 14 days).

[figure not shown]
[figure not shown]
Plot of mean (+SE) cytokine concentrations and its fold change from baseline will be generated for baseline and all cycles.

[figure not shown]
Absolute eosinophil count, absolute lymphocyte count, and their ratios of C1D8 / baseline will be summarized with descriptive statistics: n (number of non-missing data), arithmetic mean, standard deviation, SE, CV%, median, 25th and 75th percentiles, minimum, and maximum.

Plot of mean (+SE) absolute lymphocyte counts and absolute eosinophil counts versus nominal time will be generated for baseline and Cycle 1. Fold change from baseline plots will also be generated. Baseline is the last observation prior to first dose within 2 weeks (or 14 days).

Plot of mean (+SE) eosinophil trough count and its change from baseline will be generated for baseline and all cycles.

Rounding for the reporting of parameters will be to 3 significant digits. Percentages presented in tables such as CV% will be rounded to one decimal place. The same convention will be followed for descriptive statistics, except for n, which will be rounded to the whole value. Descriptive statistics will not be performed if $n < 3$ and summary tables will only include median, minimum, and maximum.

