
Objectives:
	
 • To evaluate whether programmed cell death ligand 1 (PD-L1) expression on tumor cells (< 1% vs ≥ 1%) using the PD-L1 immunohistochemistry (IHC) 28-8 pharmDx assay is a predictive biomarker for ORR, PFS, and OS in patients with previously untreated advanced RCC • To characterize changes in cancer-related symptoms and quality-of-life in patients with previously untreated advanced RCC using the National Comprehensive Cancer Network/Functional Assessment of Cancer Therapy (NCCN/FACT) Symptom Index for Kidney Cancer (FKSI-19) 
[REDACTED]
 
[REDACTED]
 
[REDACTED]
 
[REDACTED]
 
[REDACTED]
 
[REDACTED]
 
[REDACTED]
 
[REDACTED]
 
[REDACTED]

Duration of Treatment:
	
Patients will be treated until a maximum of 2 years (Arm A only), disease progression per mRECIST 1.1 in the absence of clinical benefit as determined by the Investigator, death, unacceptable toxicity, symptomatic deterioration, the Investigator’s decision to discontinue treatment, patient decision to discontinue treatment or withdraw consent, loss to follow-up, or termination of the study by the Sponsor. Treatment may continue beyond progression if the patient is receiving clinical benefit as determined by the Investigator.

Study Population:
	
Patients aged 18 years and older with advanced or metastatic, histologically confirmed RCC (advanced RCC) with a clear-cell component, who have not received prior therapy for the treatment of RCC.

Number of Patients (Planned):
	
Approximately 600 patients (including at least 500 patients with IMDC intermediate- and poor-risk and approximately 100 patients with IMDC favorable risk) with previously untreated advanced RCC will be randomized (300 per arm).

Number of Study Sites:
	
123 sites

Countries/Regions:
	
Global

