7.8.2 Evaluation of ADA

The following analyses will be conducted for anti-NKTR-214/anti-PEG, anti-IL-2 and anti-nivolumab, separately.

- Safety: All patients with ADA as mentioned above will be assessed for potential infusion related reactions under NKTR 214 safety events and will be compared against ADA negative patients, where infusion related reaction events that start after study drug administration on the same day or next day will be included.
- Efficacy: Objective response rate will be presented by ADA status.
- Concentration: Pre-dose NKTR-214 RC and pre-dose NKTR-214 AC concentrations will be summarized by ADA status.

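### The NKTR-214 outlier rule can be read as two formulas and counts unquantifiable samples as zero, so where few samples are quantifiable it would delete genuine concentrations

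*SAP*

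**What the plan says.** SAP 12.1.1 handles NKTR-214-RC, NKTR-214-AC and Total-PEG in one bullet. Three statements in it work together.

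- On low values: "below the limit of quantification (BLQ) values will be considered as zero".
- On zeros, which are left out only of the geometric mean and its CV%: "zero values will be included for all other summary statistics and the number of non-zero concentrations will be reported".
- On outliers: "Samples with concentrations 5 x higher than mean + standard deviations (SD) for all samples at that time will be considered outliers". Such samples are "not included in analyses and summary statistics and plots".

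The rule has no lower limit, no minimum number of quantifiable samples, no need for an identified error, and no summary with and without the deleted values. The reasons for not using data are to be discussed in the clinical study report. The nivolumab bullet in the same section has no outlier rule and sets BLQ values after the first pre-dose sample to half the quantification limit.

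SAP 12.1 plans the arithmetic mean, SD, geometric mean, median, range and number of non-zero values at each nominal time, together with by-patient listings. On anti-drug antibodies (ADA), SAP 7.8.2 adds: "Pre-dose NKTR-214 RC and pre-dose NKTR-214 AC concentrations will be summarized by ADA status".

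**The concern.** The cut-off is built from all samples at the time point. Read with the zero convention in the same bullet, that includes the BLQ zeros. When most samples are BLQ, the mean and SD shrink toward zero and the cut-off shrinks with them, so an ordinary measurable concentration can be classed as an outlier.

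This could happen at pre-dose times. Protocol Table 6 schedules pre-dose NKTR-214 samples at Cycle 1 Day 22 and on Day 1 of Cycles 3, 6, 9, 12 and 15, about three weeks after the previous dose. Protocol 2.2.3 puts the peak of the active species at 26 to 48 hours after infusion. The number of non-zero values, the maximum and the mean would then be computed after the measurable samples had been removed, and would understate measurable drug.

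The wording is a separate defect. Two programmers could write two different formulas from the sentence and produce different tables, whatever the BLQ rate.

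**Working it through.** The plan gives no figure for this rule, so there is none to reproduce. The rule was applied directly.

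**Inputs.** BLQ = 0 and zeros kept in mean and SD (SAP 12.1.1). Pharmacokinetics in Arm A only (SAP 5.3), so at most about 300 samples per time point (Protocol synopsis, 300 per arm). The share of samples quantifiable, p, and the spread of the quantifiable values are not in the documents. They are assumed: p from 1% to 100%, and log-normal values with CV 30%, 60% or 100%.

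**Readings.** A: delete if value > 5 x (mean + SD). B: delete if value > mean + 5 x SD.

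**Equal values.** Let a share p have the common value c and the rest be 0. Then mean = pc and SD = c√(p(1−p)).

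- A deletes every quantifiable value when 5(p + √(p(1−p))) < 1. Squaring √(p(1−p)) = 0.2 − p gives 2p² − 1.4p + 0.04 = 0, so p = (1.4 − √1.64)/4 = 2.98%.
- B does so when 1 − p > 5√(p(1−p)), that is 1 − p > 25p, so p < 1/26 = 3.85%.

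**Example with 300 samples, sample SD, c = 1.** With 8 quantifiable, mean = 0.0267 and SD = 0.161. Cut-off A is 5 x 0.188 = 0.94, below 1, so all 8 go and the non-zero count falls from 8 to 0. With 9 quantifiable, cut-off A is just above 1 and none goes. For B the limit is 11: mean 0.0367, SD 0.188, cut-off 0.98.

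A lone quantifiable value is always deleted once there are 35 samples (A) or 27 (B).

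**Varying values.** 300 samples, 3,000 runs, fixed number quantifiable. The table gives the mean share of real values deleted, as the range over the three CVs.

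| Quantifiable | Reading A | Reading B |
|---|---|---|
| 1% | 69-98% | 71-99% |
| 2% | 43-73% | 47-83% |
| 3% | 30-41% | 34-58% |
| 5% | 10-17% | 21-24% |
| 10% | 0.3-6.3% | 2.5-9.7% |
| 20% | 0.0-1.9% | 0.1-3.9% |
| 50% | 0.0-0.3% | 0.0-1.1% |
| 100% | 0.0-0.1% | 0.0-0.5% |

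Letting the number quantifiable vary at random around the same share gives, over both readings, about 11-24% at 5% and 0.5-10% at 10%.

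**Difference between readings with nothing BLQ.** With 270 samples, all quantifiable, CV 100%, A deletes 0.15 samples per time point and B deletes 1.4.

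**Mean and SD from quantifiable samples only.** With 300 samples and 1-10% quantifiable, deletion is 0.0% at all three CVs under both readings.

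**The case against.** The strongest reply is that the harm depends on an input the documents do not supply. No BLQ rate or quantification limit is stated for any NKTR-214 analyte at any time. Wholesale deletion needs fewer than about 3-4% quantifiable, and above 20% the first reading hardly fires. The one time point where nearly all values should be BLQ is before the first dose, and a quantifiable value there may well be a true anomaly. This stands, and it makes the size conditional.

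There are also safeguards. The study report must discuss unused data, and the outlier rule does not remove values from the by-patient listings. So deletions would be disclosed and the values would not be lost. That also stands, but disclosure does not restore the summaries, and the disclosed reason may be no more than the cut-off itself.

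Three stronger readings are tempting and are not supported.

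- A reader might infer that the rule would erase an ADA effect on exposure. SAP 7.8.2 plans a summary of pre-dose concentrations by ADA status; its wording about comparing groups belongs to infusion-related reactions. SAP 12.1.1 does not say that its rule governs 7.8.2, and no document gives the direction or frequency of such an effect.
- A reader might infer that deletion always biases downward. Dropping high values can only lower a mean, but dropping an erroneous one reduces bias.
- A reader might infer that nothing is gained, because medians and geometric means are planned. Where most samples are BLQ, the median is zero with or without deletion, and the geometric mean rests on the few non-zero values.

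**Conclusion.** The concern holds as a minor, conditional defect. Two parts rest on the text alone: the sentence fits two formulas that delete different samples, and values are removed on a high-side cut-off without any identified error. That BLQ zeros enter the cut-off is the plain reading of the bullet, although the outlier sentence does not repeat the zero convention.

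The size depends on the assumed quantifiable share. Below about 3.0% (A) or 3.8% (B), equal values are all lost. At 5% roughly 10-24% of real values go, and at 10% between 0.3% and 10%. From 20% upward deletion is rare under A, at most about 2%. The documents do not show that a time point with so few quantifiable samples will occur; pre-dose samples three weeks after dosing are where it could. The pre-dose summaries by ADA status are affected only if the rule is applied there.

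The primary and key secondary endpoints are not touched.

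**What to change.** Amend SAP 12.1.1 as follows.

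1. Exclude a concentration only for a documented dosing, sampling or assay error. SAP 12.1 already excludes samples collected outside the allowed time windows.
2. Flag statistically extreme values, keep them in the main summaries and plots, and show each affected summary with and without them. State that this also holds for the pre-dose summaries in 7.8.2.
3. If a numerical flag is kept, write one explicit formula and compute its mean and SD from quantifiable samples only.

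A flag of this kind cannot fire when the values it uses number fewer than 35 (A) or 27 (B), by the lone-value limits shown in the working. With 300 samples, 27 is 9% quantifiable. At sparse time points, errors must therefore be found through item 1.

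The cost is SAP wording and a few extra table rows. The downside is that a rare unexplained high value may pull an arithmetic mean, which the with-and-without summary would show.

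### SAP 12.2 sets a below-quantification baseline sCD25 to 0, which leaves the planned fold change undefined for that patient

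*SAP*

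**What the plan says.** SAP 12.2 treats sCD25 and the cytokines together. For each analyte it lists and tabulates concentrations, plus "fold change from baseline at each nominal PK sampling time and maximum fold change and time of maximum fold change". The statistics include arithmetic and geometric means, median, quartiles, minimum and maximum. Fold-change plots are also planned. Baseline there is the last observation before the first dose, within 14 days.

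The BLQ rules then differ by analyte:

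- **sCD25, Cycle 1 pre-dose:** "all Cycle 1 pre-dose concentrations that are BLQ will be set to 0".
- **sCD25, every other sample:** "all other concentrations that are BLQ will be considered missing", and "Missing concentration values will not be included in the descriptive statistics".
- **sCD25, zeros:** left out of the geometric mean and geometric CV. Nothing is said about zeros in a ratio.
- **Cytokines:** every BLQ value is set to the LLOQ.

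SAP 6.4 adds that missing data not covered by its listed rules are not imputed.

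**The concern.** Fold change divides each later value by the patient's own baseline. A rule that can make the baseline exactly 0 breaks the measure it is meant to serve. The programmer must then improvise by dropping the patient, substituting a value or carrying an infinite ratio, and each choice gives a different table. If such patients are dropped, the loss is not random, because it falls on those with the lowest baseline sCD25. The treatment of later BLQ values adds a second, smaller distortion at individual visits. What is at stake is the reliability of one descriptive pharmacodynamic summary in Arm A.

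**Working it through.** The documents state no figure on this point, so there is nothing to reproduce. The check has two parts.

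**1. Applying the rule (no assumptions needed).** Fold change = later value / baseline. Protocol Table 6 has pre-dose PK samples on both Cycle 1 Day 1 and Cycle 1 Day 22, and a cycle is 6 weeks. The Cycle 1 pre-dose rule therefore covers both days if read literally. Some columns of Table 6 are redacted, so whether sCD25 is drawn on Day 22 cannot be seen. SAP 12.2 does refer to each nominal PK sampling time.

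| Baseline | Later sample | Result |
|---|---|---|
| BLQ, set to 0 | quantifiable | x/0, infinite |
| BLQ, set to 0 | Day 22 pre-dose BLQ, set to 0 | 0/0, not a number |
| BLQ, set to 0 | other BLQ, missing | missing |
| quantifiable | Day 22 pre-dose BLQ, set to 0 | 0 |
| quantifiable | other BLQ, missing | dropped |

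No row with a BLQ baseline gives a usable ratio, so the maximum and its time are undefined as well. Under the cytokine rule every row is finite.

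**2. Size of the bias (illustration only).** The documents give no sCD25 LLOQ, BLQ rate, variance or expected induction. Assumed:

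- log-normal values with log-SD 0.5;
- baseline/post-dose correlation 0.5 or 0.8;
- baseline BLQ proportion 5%, 10% or 20%, with the same LLOQ at all times;
- true geometric mean fold change f of 0.8, 1, 2 or 5.

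Each scenario simulated 1,000,000 patients (300,000 for the maximum, over five post-dose times).

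One scenario in full (correlation 0.5, 20% baseline BLQ, f = 1):

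- True mean fold change: 1.134 in all patients, 1.025 in those with quantifiable baseline.
- Later BLQ dropped: 1.100. That is +7.4% against the quantifiable-baseline group, and 1.100/1.134 - 1 = -3.0% against all patients.
- Later BLQ set to 0, as on Day 22: 14.1% of the group are BLQ, so 1.100 x (1 - 0.141) = 0.945, and 0.945/1.025 - 1 = -7.8%.
- BLQ set to LLOQ: 1.096, and 1.096/1.134 - 1 = -3.4% against all patients.

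At f = 5 with the same settings, the means are 5.666 (all), 5.119 (quantifiable baseline) and 5.119 (as planned). The planned summary shows no error within the group, and 5.119/5.666 - 1 = -9.7% against all patients.

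Ranges of error in the mean over the scenarios:

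| Comparison | f = 0.8 | f = 1 | f = 2 or 5 |
|---|---|---|---|
| Later BLQ missing, against quantifiable-baseline group | +2.3% to +13.8% | +1.0% to +7.4% | 0.0% to +0.3% |
| Day 22 BLQ set to 0, same group | -5.5% to -17.4% | -1.8% to -7.8% | 0.0% to -0.2% |
| Planned summary, against all patients | +1.1% to +2.9% | -0.2% to -3.0% | -1.2% to -9.7% |

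For maximum fold change in patients with a quantifiable baseline, the excess was below 0.02% in the scenarios run. Under BLQ = LLOQ the error against all patients ran from about -7% to +5%.

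**The case against.** The strongest reply is that this is descriptive output with no test or alpha attached. Values are listed by patient and the number of non-missing results is tabulated, so lost ratios would be visible. BLQ baselines may be rare or absent. A pre-dose zero also matches the SAP's handling of nivolumab and the NKTR-214 analytes. Parts of the relevant text are redacted (the subsections after SAP 5.3.4, part of the 12.2 heading, columns of Protocol Table 6), and a derivation rule could sit there. Finally, LLOQ substitution is itself biased.

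Much of this stands. It limits the importance of the point, and the finding is confined to the visible text. It does not remove the defect, because the visible rule is explicit and gives a zero denominator. The analogy with the administered drugs is weak: their true pre-dose concentration is expected to be zero, and SAP 12.1 plans no fold change for them.

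A reader might go further and infer that the remaining patients' fold changes are biased upward. The documents do not support that as a general statement. The upward shift needs later BLQ values that are set to missing. In the simulation it was negligible at true fold changes of 2 or more and for the maximum. A literal Day 22 zero or the loss of low-baseline patients can pull the summary down. Nor do the documents show that the lost patients have the largest induction.

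**Conclusion.** The point holds as a narrow defect. For any patient with a BLQ baseline sCD25, the stated rule leaves fold change, maximum fold change and its time undefined, and no visible text says what to do. That conclusion rests on no assumption beyond the baseline being a Cycle 1 pre-dose sample.

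The number of patients affected is unknown. If 5% to 20% of the 300 planned in Arm A had a BLQ baseline, it would be 0.05 x 300 = 15 to 0.20 x 300 = 60. Both the rate and full sampling are assumptions, since Protocol 5.9 and 5.10 let some sites opt out, and the true number could be zero. These are not estimates from the documents. The bias at individual time points is likewise conditional, in direction and in size, on the BLQ rate and the true induction.

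Priority is low: no primary or key secondary analysis is touched.

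**What to change.** In SAP 12.2, for sCD25 fold change, replace the zero/missing rule with a single non-zero rule covering baseline and all post-baseline samples, namely the cytokine rule already in that section (BLQ set to the LLOQ). Report the number of BLQ values at baseline and at each time point beside the fold-change summaries.

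The cost is a sentence in the SAP and a count in the tables. There is a statistical downside. If the true baseline b is below the LLOQ, then x/LLOQ is smaller than x/b, so fold change is understated for a patient with an imputed baseline and a quantifiable later value x. Some residual bias remains. The BLQ counts let a reader judge how much that matters.
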